5.1 Project plan outline

This 30-month project uses a mixed-methods design and comprises six complementary work packages (WP) that are aligned with the main steps of SROI evaluations (11): a succinct evidence synthesis (WP1); primary qualitative and quantitative data collection on intervention outcomes, costs, and social value (WP2-4); estimation of SROI (WP5); and consultation on practice use of study outputs, and on the blueprint of an online social value bank (WP6). As the study comprises complementary WPs, methods, analyses and study population vary between WPs therefore these are described specific to each WP, where appropriate.

The population in focus, i.e. target population of AFCC interventions, is current and future older adults living in urban, rural and coastal areas in England. 'Stakeholders' indicate policy and practice professionals, volunteers, and wider community, affected by AFCC. Selection of stakeholders and members of the public is critically important for equity reasons, given the weight of their value judgement in the SROI analysis.

For qualitative components we will work with key contacts and use purposive sampling and snowballing to recruit representative samples. For quantitative components we will recruit a representative panel of older adults with support from a specialised survey agency, combined with working with key contacts in our case study sites. The outcomes of interest are individual and community level health related outcomes (see ToC). The intervention will be the AFCC initiatives in the case study sites (n=4) with a specific focus on local priority areas of age-friendly work (e.g. housing, transport, arts & leisure; see WP 2 below), out of which 2-3 highly specific age-friendly projects (e.g. an age-friendly housing development) will be chosen from across the 4 sites (see WPs 4 & 5 below).

5.2 WP1 – Reviewing the evidence (months 1-4)

We will synthesise existing evidence of the social value of AFCCs (Objective 1) as the initial building block to address our first research question: What are the preferred health-related outcomes of AFCC interventions and their social value? We will describe and summarise: i) the extent to which SROI methods are being used to evaluate age-friendly initiatives; ii) the outcomes being assessed and the results of the analyses; iii) the quality of existing studies. The PROSPERO registered protocol (16) is summarised below. We will follow guidance for systematic review of economic evaluations for the design and will follow PRISMA for reporting.

Participants/population: Older adults, living in the community or an institution. Definitions of "older adults" vary; we will adopt those used by individual studies and describe diversity and representativeness of participants.

Intervention/exposure: Any place-based intervention designed to achieve outcomes in relation to ageing well that has been assessed using SROI analysis.

Comparator(s)/control: Studies with any type of comparators/controls (including those where no comparator groups are presented) will be included.

Outcomes: All outcomes relating to ageing well, measured at individual or community levels. They will include, but not be restricted to, healthy ageing, wellbeing and health in later life, active ageing, quality of life, social isolation, loneliness, independence.

Searches: Publication period from 1996 until present using key search terms related to 'Social Return on Investment', such as 'SROI' or 'social value', and a comprehensive list of age-related terms. For the scientific literature, standard databases will be searched, i.e. MEDLINE, Web of Science, Scopus, PsycINFO, Embase, CINAHL and the Cochrane Library. Following Banke-Thomas et al. (20), SROI studies in the grey literature will be identified via review of titles, abstracts or executive summaries or full text of articles found through web search (Google), or from SROI focused databases (e.g. SROI Network; New Economics Foundation; evidence.nhs.uk). We will consult our network of topic experts to identify further resources.

Data extraction & Quality assessment: Search results will be imported into EndNote and two reviewers will screen titles and abstracts to determine in-/exclusion. Any conflicts will be resolved in discussion with a third reviewer. Studies will be excluded if they meet one or more of the following criteria: i) they do not refer to clearly defined older population(s); ii) They do not refer to clearly identified intervention/programme(s); iii) They do not present clearly identified outcomes in relation to ageing well.

The following data will be extracted by one reviewer and checked by another after pilot testing of the data extraction instruments on a subset of the most "comprehensive" studies: year of publication; location (country) and setting of the intervention; details of the study design; aim of intervention or programme and period over which it was delivered; stakeholders included in the study (i.e. older residents, wider community, volunteers, professionals in policy and practice that are affected by the intervention/programme); source and method of data collection for prioritisation and measurement of outcomes and costs/resources; approach used for the attribution of SROI ratio; discussed strengths and limitations.

Quality will be assessed independently by two reviewers using the SROI quality framework assessment tool developed by Hutchinson et al. (21), supplemented by Krlev et al. (22). Disagreements will be resolved by a third reviewer.

Strategy for data synthesis: A narrative synthesis will also be developed in accordance with the guidelines developed by Popay et al. (29), following the research question for the review. Preliminary searches indicate that it is unlikely that there will be enough studies and/or homogeneity for any quantitative analyses.

5.3 WP2 – Identifying local priorities & outcomes (months 1-12)

The objective of this WP is to develop a list of prioritised outcomes of AFCC interventions through engagement with practice-based stakeholders and members of the public. As with WP1, this specifically relates to our first research question and constitutes a core building block for the next phase (WP3).

Site selection: The fieldwork will be carried out in four research sites: Suffolk (coastal), Liverpool (urban), Kelsall/Cheshire (rural) and Buckden/Cambridgeshire (rural). Sites were chosen to reflect a sample that

was diverse in terms of location, rural/urban classification, administrative geographies (county/city/town/parishes); population numbers, demographic make-up (ethnic groups), age distribution, and socio-economic characteristics/Index of Multiple Deprivation (IMD).

Liverpool and Cheshire (where Kelsall is located) are both operating within a context where WHO's AFCC framework has been explicitly adopted. In contrast, Buckden and Suffolk are not part of explicit WHO-based AFCC initiatives. Rather, they have embedded age-friendly principles in their strategic directions and operational priorities. Across all sites, we will work with relevant authorities, taking account of the policies and practices of health commissioners, providers and other public bodies, to capture context.

We will map age-friendly work in the four sites through documentary analyses and local interviews to understand context, inputs, outputs, and actual and expected outcomes and longer-term impacts. This will inform site-specific ToCs. The latter will be locally specific versions of the overall AFCC ToC (see Section 3), an evidence-informed framework based on previous work of the Cambridge team on AFCCs (30-32) and the wider AFCC literature. It will be revised on an ongoing basis as findings from this study become available.

We will identify priority age-friendly themes (e.g. housing; transport; see ToC, Section 3) in each site. This will involve carrying out local community surveys. The survey has already been completed in Liverpool. In this instance, it was commissioned by the City Council, and it had been directly informed by the research team in light of the proposed study's objectives and data requirements. A detailed report of findings is available (33). Building on the surveys' findings, we will run local stakeholder workshops to reduce the priority themes identified to a maximum of three priority age-friendly themes in each site, guided by both scientific and pragmatic criteria (e.g. availability or collectability of outcomes data for each theme; wider relevance beyond the research site). These three site-specific priority themes will be the focus of WP3-WP5.

Identifying priority outcomes: Findings from WP1, analysis of local documentary evidence, survey data (see above), and interviews with local practice-based stakeholders and older residents will serve to develop an initial long list of health-related outcomes for the three priority themes in each site. Guided by the principles and approach of the Core Outcome Measure in Effectiveness Trials (COMET) initiative (http://www.comet-initiative.org/), we will produce a reduced list ('shortlist') of prioritised health-related outcomes for the valuation exercise using nominal group consensus methods. We will start with local stakeholders (n=6-8 participants/group), followed by validation using a 2-round Delphi panel including national stakeholders. The validation with national stakeholders is to ensure that selected outcomes are ones that are considered priorities beyond specific local contexts.

There is no standard method for establishing Delphi panel size (34, 35). Given the scope and resources of the study, a panel size of n=48 seems appropriate. This will include one representative respectively for 75% of the 32 members of the Network of AFCs in England (n=24), the group most directly affected and with direct experience of AFCC initiatives. Its number of panel members (n=24) will be matched by members (n=24) from the following groups: organisations working with older people (e.g. Age UK); organisations working with local/rural communities on realising their priorities (e.g. Action with Rural

Communities (ACRE)); health and social care sector (e.g. community nurses; carers); experts in social value (e.g. HACT); researchers in ageing.

Identifying interventions: The interventions will be the AFCC initiatives in the case study sites (n=4), with a specific focus on respective local priority areas of age-friendly work (e.g. housing, transport, arts & leisure) and consideration of inequalities. Consulting with stakeholders and members of the public across the research sites, we will select a total of 2-3 highly specific age-friendly projects per site within the priority areas of work (e.g. an age-friendly housing development) for later assessment (see WPs 4 & 5).

With input from the local stakeholders, we will identify existing data sources for the priority health-related outcomes and we will seek stakeholders' advice on additional data to be collected, and how we can best do this in efficient yet robust, locally appropriate and inclusive ways. Consultations to evidence outcomes (in particular for outcomes for which there is no routine monitoring) will take place later in the project (WP5) to give the research team time to analyse and integrate findings from WP1 and WP2 - a necessary step before evidencing outcomes.

5.4 WP3 – Valuing outcomes (social value bank) (months 11-26)

This WP will address our third objective, i.e. to attribute monetary values to outcomes using preferencebased valuation with older adults. It will allow us to describe what the preferred health-related outcomes of AFCC interventions are and their social value (our first research question).

In the Discrete Choice Experiment (DCE) (36), we will ask a representative national panel of older adults (55+yrs) to state their preferences for different combinations of outcomes on the short list developed in WP2. The outcomes will be valued using willingness to pay (WTP) methods via the inclusion of a payment vehicle (e.g. additional council tax payment per month) as an attribute in the DCE.

DCE Design: DCE is a quantitative technique for eliciting individual preferences. It allows researchers to uncover how respondents value selected characteristics (in this case, outcomes) of a programme, product or service by asking them to state their preferences over hypothetical alternatives (36). Each alternative is defined by several characteristics, known as attributes with multiple levels, and the responses are used to determine whether preferences are significantly influenced by the attributes and also their relative importance. DCEs are grounded in theories which assume that i) alternatives can be described by their attributes, ii) an individual's valuation depends upon the levels of these attributes, and iii) choices are based on a latent utility function (37). The relative importance of the attribute's levels in driving choice and trade-offs individual make when choosing one alternative over another are estimated through regression analysis of the choice data (38).

DCE Survey: The choice of attributes and levels for the survey will be based on the extensive qualitative work with residents and professional stakeholders carried out in WP2, and combined using an orthogonal or D-efficient statistical design to optimise the precision of the preferences estimates (38). This will be informed by the findings of WP1 and the WHO core AFCC indicators (39), before validation by our case study sites' stakeholders and contacts within the UK Network of Age-Friendly Communities. The survey will present pairs of hypothetical communities with varied age-friendly characteristics.

The process in WP2 for reducing item numbers to a prioritised list will consider the likely independence of outcomes when grouping them into themes and deciding which prioritised outcomes to take forward as attributes into the DCE. For the DCE survey, respondents will be asked to indicate their preferred alternative between a number of different outcomes (with consideration of COVID impact), i.e. a discrete choice between attributes such as access to transport; safety at home; opportunities for employment; reduced risks, healthy behaviours, sense of belonging, etc. From this choice data, we will estimate their WTP for improvements in different outcomes, i.e. bespoke social values for the outcomes. When undertaking the statistical design for the DCE, we will consider whether attributes are likely to be interdependent (based either on evidence gathered in WPs1-2 or on underlying theory). We will consider including interaction effects between attributes in addition to the main effects for each attribute in both the statistical design and analysis, for any attributes for which we anticipate a likely dependent relationship.

The survey will be administered online (with phone assistance where needed) or face-to-face with a paper-based option to accommodate varying capabilities. The survey will comprise background information about the project and ethics approval, followed by an informed consent page, then questions on respondents' demographic characteristics, health, functional ability, and quality of life. Subsequently, respondents will be shown instructions about the task and a warm up task before answering the survey. At the piloting phase, following Mulhern (40), multiple choice questions about the difficulty of the tasks will be included along with a free-text question to understand respondents' opinions of the survey questions and the content in general. These questions provide data relating to the difficulty of the choice sets and the functioning of the survey.

Recruitment of respondents: A population panel representative of the older adult population in England (by age, gender, urban/rural divide) will be selected through a panel company (e.g. SurveyEngine,) to determine average preferences. Sampling theory does not provide definitive guidance on the minimum sample size required for a DCE. To ensure precise (statistically significant) estimates are obtained from the DCE, the minimum sample size depends on a number of criteria including choice task complexity, attribute and level number, and the desire to conduct subgroup analysis. The sample size (estimate n=400) will be based on the commonly applied rule of thumb (41) once the number of levels and attributes are known. Simulation studies suggest little if any improvement in precision is achieved for sample sizes beyond 300 participants (42) when the study aim is to estimate "average" utility weights for a representative sample. Based on approximately 17,1M adults aged 55+yrs in England (43), for a \pm 5% margin of error at a 95% confidence level, a minimum sample of 376 would be required (making the most conservative assumption of equal preferences for a dichotomous choice). Therefore, we target a sample size of 400 for the DCE public sample.

We will also aim to recruit a separate sub-sample of frail older adults (estimate n=40) via our case study site contacts and PPI contributors to determine if there is consistency in preference in this sub-group whose ability to benefit from AFCC interventions (i.e. in terms of health and well-being benefit) is crucial to minimise the potential for intervention generated inequalities (44). Frail older adults and others with specific needs will be invited to draw on the support of a carer, e.g. to help them set up a phone conversation. The DCE is planned mostly as an online survey, with phone supported completion of either online or paper-based versions. We will monitor how the situation evolves and adjust options for completing the survey (late 2021) in accordance with participants' capacities and preferences.

WTP estimates will be based on data derived from the DCE survey, i.e. we will estimate 'average' WTP estimate for the representative sample of older adults; we will not adjust for ability to pay. However, we will describe the sample according to socio-demographic factors (including household income), and explore whether preferences differ by wealth or income (we would expect those with higher income to be WTP more). We will also explore other equity measures, using relevant tools and guidance.

The choice data collected from the DCE will be analysed using multinomial logit regression with preference heterogeneity explored using its more generalised forms (e.g. mixed logit or latent class analysis). This will enable an estimate of the trade-off participants are willing to make between different community attributes (i.e. outcomes) and also their WTP for improvements in different outcomes.

Assessing stability of preferences: It is likely that the preferences identified in the DCE (Nov '21 – Feb '22) will be affected by the status of the COVID-19 pandemic at the time of data collection, i.e. whether the situation is stable or not (e.g. if a "new normal" has set in with regard to social distancing rules and risks; or if a vaccine is available). To address this uncertain situation, we will explore the feasibility of repeating the DCE on the same sample 6-8 months later, acknowledging there will be non-random drop out due to the sample characteristics (i.e. many of whom will be frail(er) and some will have died). We will also draw on our PPI contributors to help us ascertain the stability of preferences for those groups most likely to be affected by the pandemic situation.

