5.5 WP5 – Assessing SROI of specific interventions (months 22-28)

The SROI ratio is calculated by dividing the overall value of the outcomes by the cost of the AFCC intervention [(positive benefits – negative benefits)/costs] to represent the value created. The value of the benefits will be derived from WTP in WP3 and the costs of interventions will be derived in WP4. Although the idea of 'cashable and non-cashable' value is not in the spirit of SROI, direct monetary benefits (where available) will be described in a fully disaggregated way alongside accrued social value for relevant outcomes. Alternative financial proxies will be examined through sensitivity analysis.

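### The DCE panel is made representative on age, gender and urban/rural only, although the plan expects WTP to rise with income, so the average social values depend on an uncontrolled income mix

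*Protocol*

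**What the plan says.** Protocol section 5.4 (WP3), under recruitment, defines the panel: "A population panel representative of the older adult population in England (by age, gender, urban/rural divide) will be selected through a panel company". Three variables are named; income, wealth, education and deprivation are not among them.

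The values come from a cost attribute, through "inclusion of a payment vehicle (e.g. additional council tax payment per month) as an attribute in the DCE". The quantity to be estimated is then stated: "we will estimate 'average' WTP estimate for the representative sample of older adults; we will not adjust for ability to pay". The plan adds the parenthetical expectation that "we would expect those with higher income to be WTP more". Its commitment on income is to "describe the sample according to socio-demographic factors (including household income), and explore whether preferences differ by wealth or income".

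Section 5.5 (WP5) gives the downstream use: "The value of the benefits will be derived from WTP in WP3". Those benefits, net of negative ones, are divided by costs to give the SROI ratio.

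**The concern.** A sample average estimates a population average if the sample matches the population on what drives the outcome, or is weighted to match. The plan controls three variables and leaves free one that it expects to move WTP. Age, gender and urban/rural status control income only indirectly.

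At stake is what the social value bank can claim. Its entries are meant to be average values for older adults in England, and the case-study SROI ratios are built on them. If the panel is richer or poorer than the 55+ population, the averages carry that difference. The planned description of household income would show it but leave the headline values unchanged.

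Timing matters too. Weights can be added at analysis, but a quota has to be set before recruitment, and weights cannot make up for income groups that were barely recruited.

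**Working it through.** **The plan's own figure.** The only calculation nearby is the sample size in section 5.4. For a ±5% margin at 95% confidence and a proportion of 0.5, n = 1.96² × 0.25 / 0.05² = 384.1, so 385; the finite-population correction for 17.1 million changes nothing visible (384.14). The protocol states 376, which is 9 lower (2.4%). The target of 400 gives 1.96 × √(0.25/400) = ±4.9% and covers either figure. This margin describes sampling error only. It says nothing about the panel's income mix, and the point below does not depend on it.

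**Inputs for the income question.** From the documents: the three representativeness variables, the expected rise of WTP with income, the use of the sample average, and its passage into the SROI numerator. Not in the documents, so assumed: how steeply WTP rises with income, and how far the panel's income differs from the population's.

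**Illustration 1, elasticity.** Scale all incomes by the same factor. Shift in WTP = (1 + income deviation)^elasticity − 1.

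| Panel mean income | Elasticity 0.5 | Elasticity 1.0 |
|---|---|---|
| 10% above population | 1.10^0.5 − 1 = 4.9% | 10% |
| 20% above population | 1.20^0.5 − 1 = 9.5% | 20% |

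For a poorer panel the shifts are of similar size and negative: 0.90^0.5 − 1 = −5.1% and 0.80^0.5 − 1 = −10.6% at elasticity 0.5, and −10% and −20% at elasticity 1.0.

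**Illustration 2, two income halves.** Let the upper half have r times the WTP of the lower half, and let h be the panel share from the upper half (population 0.5). Shift = [(1 − h) + h·r] / (0.5 + 0.5·r) − 1.

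| r | h = 0.4 or 0.6 | h = 0.3 or 0.7 |
|---|---|---|
| 1.25 | ±2.2% | ±4.4% |
| 1.5 | ±4.0% | ±8.0% |
| 2 | ±6.7% | ±13.3% |
| 3 | ±10.0% | ±20.0% |

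For example, r = 2 and h = 0.7 gives 1.7/1.5 − 1 = 13.3%. At h = 0.5 the shift is zero.

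**Illustration 3, pooled logit.** WTP is the attribute coefficient divided by the cost coefficient, with the sign reversed. Let the halves differ only in the cost coefficient (1 in the lower half, 1/r in the upper) and approximate the pooled cost coefficient by the share-weighted mean. WTP is then proportional to 1/[(1 − h) + h/r]. At r = 3 this gives 1.875 at h = 0.7, 1.25 at h = 0.3 and 1.5 at h = 0.5, so the shift runs from −16.7% to +25.0%.

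**Passage into SROI.** If all WTP values shift by the same percentage, the WTP-valued part of the numerator shifts by that percentage too. A uniform shift requires income to act through the cost coefficient, which divides every attribute coefficient alike.

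**The case against.** The strongest reply has three parts.

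- **Weighting belongs in an analysis plan, which is not shown.** This stands for weighting: the protocol neither plans nor excludes it. A reader might infer from "we will not adjust for ability to pay" that the average is fixed as unweighted. The text does not support that, because it concerns how each person's WTP counts, not whose WTPs are averaged. The reply does not cover the quota, because the protocol itself sets the recruitment variables.
- **The plan is open about income and has sensitivity analyses.** This stands in part. Section 5.4 would make an imbalance visible, and section 5.5 varies financial proxies and observed change. Panel composition is not named among those checks.
- **Nothing in the documents says the panel will be off on income.** This stands. The percentages above are conditional arithmetic, not a forecast.

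Three stronger readings are tempting and should be resisted. A reader might infer that the protocol treats income as the main driver of WTP; it states only an expected direction, in parentheses, and ranks no drivers. A reader might infer that every social value would move the same way; section 5.4 allows preferences themselves to differ by income, so values for attributes such as transport or employment could move differently. And since the sites were chosen to differ in deprivation, a reader might infer that the bias is largest at deprived sites. The protocol describes one national set of values, so a sampling error in it is the same percentage wherever it is used. The gap between a national value and local WTP is a separate transfer question, which an income quota would not remove.

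**Conclusion.** The point holds as a cheap improvement; it is not a contradiction or a misstatement in the protocol. The panel is controlled on three variables, income is not one of them, and the plan's own expectation makes the average WTP sensitive to income mix. Direction and size are unknown. With an elasticity of 0.5 to 1.0 and panel mean income 10–20% off the population, the shift would be about 5–20% in either direction, if income acts mainly through the cost coefficient. The two-halves illustration gives 2.2% to 20% over its assumed range. If the panel happens to match the population on income, the shift is zero.

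**What to change.** 1. Add a household-income-band quota to the panel brief, or a similar socio-economic quota on a variable the panel company already holds. Household income is already to be described, so an income band is simpler than a deprivation index derived from postcode, which would need location data.
2. Report average WTP weighted to the England 55+ distribution of age, gender, urban/rural and income, alongside the unweighted estimate.
3. Keep the decision not to adjust for ability to pay, and say that it is separate from matching the sample's income mix.
4. If no quota is added, state that the values are representative on the three named variables only.

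The cost is one more quota, some missing income answers to handle, and slightly wider intervals. For two income halves and n = 400, the usual approximation for the variance inflation from weighting is the sum of (population share)²/(panel share). A 60/40 panel gives 0.25/0.6 + 0.25/0.4 = 1.042, an effective n of 384 and intervals about 2% wider (√1.042 = 1.021). A 70/30 panel gives 0.25/0.7 + 0.25/0.3 = 1.190, an effective n of 336 and intervals about 9% wider (√1.190 = 1.091). If the quota is met, this income-related loss largely disappears, which is the reason to set the quota rather than rely on weights alone.

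### The sample of about 40 frail adults is not shown to be able to determine consistency of preference, and frailty is confounded with recruitment route and site

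*Protocol*

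**What the plan says.** Protocol section 5.4 (WP3), Recruitment of respondents, sizes the main discrete choice experiment (DCE) sample on a single proportion: "5% margin of error at a 95% confidence level, a minimum sample of 376 would be required". It takes a 50% split as the worst case ("making the most conservative assumption of equal preferences for a dichotomous choice"). From this it concludes "Therefore, we target a sample size of 400 for the DCE public sample". These respondents come from a panel company and are to represent older adults in England by age, gender and urban/rural residence. The same paragraph lists the wish for subgroup analysis among the things that determine sample size.

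The next paragraph adds "a separate sub-sample of frail older adults (estimate n=40) via our case study site contacts and PPI contributors". The purpose is "to determine if there is consistency in preference in this sub-group whose ability to benefit from AFCC interventions". No precision target, margin, smallest difference of interest or definition of consistency accompanies the 40, and frailty is not defined.

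Under DCE Survey, the questionnaire includes items on respondents' "demographic characteristics, health, functional ability, and quality of life". The choice data are to be analysed by multinomial logit, with mixed logit or latent class models for heterogeneity.

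**The concern.** Determining whether preferences are consistent is a yes/no aim. A yes needs an interval narrow enough to exclude differences that matter, and a no needs reasonable power. Neither was considered for the 40, although a precision criterion was applied to the 400 in the preceding paragraph.

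The comparison also has a structural problem. One group comes through local contacts in four sites and through PPI contributors, the other from a national panel. A difference could reflect frailty, place or route of recruitment, and a larger sample would not separate these. If some panel members are frail, the 400 are not a non-frail reference group either.

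WP3 produces an average willingness to pay for each outcome, and section 5.5 (WP5) takes benefit values for the SROI ratios from it. A weakly supported statement that frail people share the average preferences could lend those values credibility for a group the protocol singles out on equity grounds.

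**Working it through.** **Inputs from the protocol (section 5.4, WP3).** Main sample 400, frail sample 40, p = 0.5, 95% confidence (z = 1.96), target margin ±5 points, and the population as stated: "Based on approximately 17,1M adults aged 55+yrs in England (43".

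**1. The plan's own figure.** n = z²·p(1−p)/e² = 1.96² × 0.25 / 0.05² = 384.1, so 385. The finite population correction at 17.1 million leaves 384.1. The stated 376 is 9 lower, about 2%, and gives ±5.05 points. A population of 17,100 would give 375.7, so a table in thousands may have been read as persons. This does not matter, since the target is 400.

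**2. The same criterion applied to 40.** Half-width = 1.96 × 0.5/√n.
- n = 400: ±4.9 points.
- n = 40: ±15.5 points.

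**3. Difference between 40 and 400.** SE = 0.5 × √(1/40 + 1/400) = 0.0829.
- 95% half-width: 1.96 × 0.0829 = ±16.3 points.
- Difference detectable with 80% power: (1.96 + 0.84) × 0.0829 = about 23 points.
- Power, Φ[(d − 1.96·SE₀)/SE₁], with SE₀ from the pooled proportion and SE₁ from the two separate proportions (0.5 + d and 0.5): 9%, 22%, 44% and 69% for d = 5, 10, 15 and 20 points.

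**4. Can agreement be shown?** Take two one-sided 5% tests with margin m and identical true preferences. The chance of success is 2Φ(m/0.0829 − 1.645) − 1, or zero if negative.

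| Margin (points) | Chance with 40 | Frail respondents for 80%, 400 fixed |
|---|---|---|
| ±10 | 0% | 461 |
| ±15 | 13% | 125 |
| ±20 | 56% | 62 |

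The last column is 0.25 / [(m/(1.645 + 1.282))² − 0.25/400], rounded up.

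**5. Repeated choice tasks (assumed; the protocol fixes no number).** With T tasks per person and within-person correlation ρ, the variance is multiplied by (1 + (T−1)ρ)/T.
- T = 12, ρ = 0.05: factor 0.129, half-width 16.3 × √0.129 = ±5.8 points, detectable difference 8.3 points, chance of showing agreement within ±10 points 91%.
- T = 6, ρ = 0.5: factor 0.583, half-width ±12.4 points, detectable difference 17.7 points, chance 0%.

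These figures still concern one choice proportion, whereas the DCE reports attribute weights and willingness to pay. Their precision cannot be computed before the design is known.

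**6. Frail members of the panel (share f assumed; the protocol gives none).** Ignoring route and site, a plain 40 versus 400 contrast shows (1−f) times the true difference. A frail versus non-frail comparison inside the panel has half-width 1.96 × 0.5 × √(1/(400f) + 1/(400(1−f))) for one choice.

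| f | A true 20 points appears as | Within-panel half-width |
|---|---|---|
| 5% | 19 | ±22.5 |
| 10% | 18 | ±16.3 |
| 20% | 16 | ±12.2 |
| 30% | 14 | ±10.7 |

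**The case against.** The best defence is that the 40 are a modest, tentative addition. The protocol only aims to recruit them, labels the number an estimate, and makes no result depend on them. Analysis detail may sit in an analysis plan that is not shown. A DCE also collects several choices per person, so single-choice figures understate its information. This last point stands: it rules out saying that the sample cannot determine consistency, and leaves only that it is not shown to be able to.

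A reader might infer several stronger things that the document does not support:
- That a non-significant difference will be read as agreement. No test, threshold or decision rule is stated.
- That the protocol calls this check crucial. The word describes the sub-group's ability to benefit, not the comparison.
- That average values will be applied to frail people only if preferences prove consistent. The average estimate is planned regardless.
- That survey mode is fully confounded with frailty. Online, phone-assisted, face-to-face and paper completion are offered generally. Carer support extends to others with specific needs, and section 7.6 lets the 40 use the electronic survey. Mode is confounded only in part.
- That frail panel members are excluded from frailty analyses. The protocol is silent on this, and its heterogeneity and equity analyses leave room for them. Under Assessing stability of preferences it also expects many in the sample to be frail or frailer, though in the context of drop-out from a repeat survey.

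None of this supplies a margin or definition for the stated aim, or removes the confounding with route and site.

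**Conclusion.** The point holds in limited form. The protocol states an aim that its comparison is not shown to deliver. On its own single-choice criterion the 40 versus 400 difference is known to ±16.3 points, with 80% power near 23 points and no chance of showing agreement within ±10 points. Under the assumed 6 to 12 tasks and correlations of 0.05 to 0.5, that chance runs from 0% to 91%, so adequacy cannot be claimed or excluded until the design is set.

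The confounding of frailty with recruitment route and site follows from the recruitment plan and needs no numerical assumption. The size of the dilution depends on the unknown share of frail panel members. This goes beyond missing analysis detail, because both the aim and the number set for it are in the protocol. A better analysis is available from items the survey already contains. It is worth correcting, but it does not threaten the main DCE estimates.

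**What to change.** In section 5.4 (WP3), Recruitment of respondents:
- Replace the aim of determining consistency with an exploratory aim: to estimate the difference in preferences between frail and non-frail respondents, with 95% confidence intervals.
- State that absence of a significant difference will not be reported as consistency.
- Classify frailty in the same way in both samples, from the health and functional-ability items already asked. Check that these items suffice for the purpose.
- Fit attribute-by-frailty interactions in the pooled data and let the scale parameter differ by recruitment source, so that noisier choices are not mistaken for different preferences.
- Report the frail versus non-frail comparison within the panel as the estimate free of route and site.
- Enter any adjustment for source or mode as an interaction with the attributes, or through scale. A respondent-level main effect is the same for both communities in a pair and cancels.

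Cost: a wording change and some extra modelling, with no extra recruitment. The conclusion becomes less definite. The within-panel estimate will be imprecise if few panel members are frail, and source interactions will then be hard to separate from frailty.
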